11.3 MONITORING AT LOCAL SITES

The frequency, type and intensity of routine and triggered on-site monitoring will be detailed in the MATIS Quality Management and Monitoring Plan (QMMP). The QMMP will also detail the procedures for review and sign-off of monitoring reports. In the event of a request for a trial site inspection by any regulatory authority the Sponsor must be notified as soon as possible.

11.4 DATA AND SAFETY MONITORING

Follow-up safety assessment will occur at day 7, 14 and 28 days. Serious adverse events (SAEs) will be collected and reported in an expedited fashion. The requirements for collection of AEs is as follows:

All SAEs

All non-serious AEs

All reports of IMP exposure during pregnancy

• All reports of misuse and abuse of an IMP, other medication errors and uses outside of what is foreseen in the protocol (irrespective if a clinical event has occurred

# 12 ETHICAL CONSIDERATIONS AND REGULATORY COMPLIANCE

This study will be carried out in compliance with the protocol and the principles of Good Clinical Practice (ICHGCP) & the Medicines for Human Use (Clinical Trials) Regulations 2004 and Amendment Regulations 2006 and is registered under the General Data Protection Regulation. The Investigator should ensure that all persons assisting with the study are adequately informed about the protocol-related duties and maintain a list of Sub-investigators and other appropriately qualified persons to whom he or she has delegated significant study-related duties. The Investigator is responsible for keeping a record of all subjects who sign an informed consent document and are screened for entry into the study. All versions of trial documents will have the relevant ethical approvals.

#### 12.1 CTA

This study has Clinical Trials Authorisation from the UK Competent Authority; MHRA. Reference: 19174/0421/001-0001

#### 12.2 ETHICS APPROVAL

The Study Coordination Centre has obtained approval from the Surrey Research Ethics Committee (REC) and Health Regulator Authority (HRA). The study must also receive confirmation of capacity and capability from each participating NHS Trust before accepting participants into the study or any research activity is carried out. The study will be conducted in accordance with the recommendations for physicians involved in research on human subjects adopted by the 18th World Medical Assembly, Helsinki 1964 and later revisions.

# **Protocol Amendments**

All protocol amendments will be approved by the sponsor prior to submission to the Ethics Committee and implementation.

#### 12.3 CONSENT

Informed consent should be obtained from each patient before enrolment into the study. However, if the patient lacks capacity to give consent due to the severity of their medical condition (e.g. acute respiratory failure or need for immediate ventilation), then consent may be obtained from a relative acting as the patient's legally designated personal representative. Further consent will then be sought with the patient if they recover sufficiently.

Due to the poor outcomes in COVID-19 patients who require ventilation (>90% mortality in one cohort5), patients who lack capacity to consent due to their disease, and for whom a relative to act as the legally designated representative is not immediately available, randomisation and consequent treatment will proceed with consent provided by a treating clinician (independent of the clinician seeking to enrol the patient) who will act as the legally designated professional representative. Consent will then be obtained from the patient's personal legally designated representative (or directly from the patient if they recover promptly) at the earliest opportunity.

Informed consent can be taken by any competent health care professional delegated by the chief investigator which can include doctors, nurses and research practitioners. If nurses or research practitioners take consent, the most up to date Legal Representative Consent Form (LRCF) should be used with the patient's treating clinician, independent of the study team, to sign as Legal Representative and the nurse/research practitioner as the person taking consent.

#### 12.4 WITHDRAWAL OF CONSENT

A decision by a participant that they no longer wish to continue receiving study treatment should **not** be considered to be a withdrawal of consent for follow-up. However, participants are free to withdraw consent for some or all aspects of the study at any time if they wish to do so. In accordance with regulatory guidance, deidentified data that have already been collected and incorporated in the study database will continue to be used (and any identifiable data will be destroyed).

# 12.5 CONFIDENTIALITY

The research team may exchange emails between themselves about the study and its data analysis. Personal addresses, postcodes, faxes, emails or telephone numbers may be used to post study documents to potential participants. The signed consent forms and completed health questionnaires will be stored safely in the locked clinical trials office, in the Hammersmith Hospital. All electronic files created for the study database will be stored in a single NHS computer, access to which is limited by a password. All electronic files/records created for the study will be password protected. The study team will ensure that the confidentiality of participant data is preserved and will only use NHS email accounts (@nhs.net) to communicate for the study. Participant names will not be disclosed and will not appear on any reports produced.

IRAS: 282552 Page **53** of **57** 

Imperial College Healthcare

The EU General Data Protection Regulation (GDPR) that came into effect on 25 May 2018 defines expanded rights for study patients. The study team will inform all participants of these rights. Personal data will be kept in line with Imperial College Healthcare NHS Trust policy for ten years.

Representatives of the sponsor will be granted direct access to original medical records for verification of trial participation and data without violating the confidentiality of these records to the extent permitted by the applicable laws and regulations. Identifiable data will be stored in the patients' medical records and NHS computers. Participants will consent to this access by signing the informed consent form.

#### 12.6 INDEMNITY

Imperial College London holds negligent harm and non-negligent harm insurance policies which apply to this study.

#### 12.7 SPONSOR

Imperial College London will act as the Trial Sponsor.

#### 12.8 FUNDING

This study is supported by the NIHR Imperial Biomedical Research Centre. The data will be collected, analysed and published independently of the source of funding; however study outcome results will be shared with Novartis or Rigel following interim analyses and prior to publication.

# 12.9 AUDITS AND INSPECTIONS

The study may be subject to inspection and audit by Imperial College Healthcare NHS Trust under their remit as sponsor to ensure adherence to GCP. The Chief Investigator will be responsible for the conduct and progress monitoring of the study.

# 13 PUBLICATIONS AND REPORTS

The Steering Committee will be responsible for drafting the main reports from the study and for review of any other reports. In general, papers initiated by the Steering Committee (including the primary manuscript) will be written in the name of the MATIS Collaborative Group, with individual investigators named personally at the end of the report (or, to comply with journal requirements, in web-based material posted with the report).

Imperial College Healthcare

The Steering Committee will also establish a process by which proposals for additional publications (including from independent external researchers) are considered by the Steering Committee. The Steering Committee will facilitate the use of the study data and approval will not be unreasonably withheld. However, the Steering Committee will need to be satisfied that any proposed publication is of high quality, honours the commitments made to the study participants in the consent documentation and ethical approvals, and is compliant with relevant legal and regulatory requirements (e.g. relating to data protection and privacy). The Steering Committee will have the right to review and comment on any draft manuscripts prior to publication.

2.7 De	escriptive statistics for outcome measures	17
2.8 Se	rious adverse events	18
3. Data a	nalysis plan - Inferential analysis	20
3.1 Pr	imary outcome of the main study - Modified WHO grading	20
3.1.1	Definition of the primary outcome	20
3.1.2	Statistical model at stage 1	20
3.1.3	Statistical model at stage 2	23

3.1.4	Model assessment of stage 2 analysis	25
3.1.5	Stage 2 exploratory analysis for primary outcome	26
3.1.6	Stage 2 subgroup analysis for primary outcome	28
3.2 Sec	condary outcomes of the main study	28
3.2.1	Severe COVID-19 within 28 days	29
3.2.2	Modified WHO COVID-19 score	29
3.2.3	Components of the modified WHO COVID-19 score	30
3.2.4	Length of stay	31
3.2.5	Continuous laboratory values	31
References.		34

STUDY MANAGEMENT

CHIEF INVESTIGATOR [name]

Imperial College Healthcare NHS Trust, Hammersmith Hospital,

[name], London

[contact], [contact]

SPONSOR Imperial College London

JRCO, Imperial College London and Imperial College Healthcare

NHS Trust; [name], St

Marys Campus

Contact: [name], Clinical Trials Manager

[contact]

FUNDER Imperial Biomedical Research Centre

CO-INVESTIGATORS [name]

[name]

[name]

[name]

[name]

[name]

[name]

[name]

[name] [name]

[name]

STATISTICIANS [name]

[name]

[name]

[name]

1. Study summary

The MATIS trial is a multi-arm, multi-stage randomised controlled trial (RCT) of ruxolitinib (RUX) and fostamatinib (FOS) for COVID-19 pneumonia. The statistical analysis plan (SAP) is based on protocol version 2.2 which can be seen for full design details.

1.1 Principal research objectives

1.1.1 Primary objective

To evaluate the efficacy of ruxolitinib (RUX) and fostamatinib (FOS) compared to standard of care (SOC) in the treatment of COVID-19 pneumonia in participants with mild disease.

1.1.2 Primary outcome of the main study

The proportion with severe COVID-19 pneumonia within 14 days of randomization. Where severe COVID-19 pneumonia is defined by a modified WHO COVID-19 Ordinal Score ≥ 5 (on the 9 point scale), comprising the following indicators of disease severity:

- Death *OR*
- Requirement for invasive ventilation plus organ support OR
- Requirement for invasive ventilation *OR*
- Requirement for non-invasive ventilation including CPAP or high flow oxygen OR
- O_2 saturation < 90% on \geq 60% inspired oxygen

1.1.3 Secondary outcomes of the main study

Each of the outcomes below at 14 and 28 days between RUX or FOS versus SOC:

- Change in severity on the modified WHO COVID-19 Ordinal Scale (3 or 4 to 5,6,7,8,9)
- Mortality (Y/N)
- Invasive ventilation (Y/N)
- ECMO (Y/N)
- Non-invasive ventilation including CPAP and high flow nasal oxygen (Y/N)
- Renal replacement therapy (Y/N)
- Venous thromboembolism (Y/N)
- Inflammatory markers CRP, LDH, ferritin, D-dimer (units)
- Length of stay (days)
- Serum creatinine (units).

• Re-admission data – were they readmitted within 28 days? (from free text in SAEs)

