#### 7.16 TREATMENT DURATION

The planned duration of treatment is 14 days. Participants may be discontinued from treatment earlier due to unacceptable toxicity or disease progression which will be recorded as Serious Adverse Event (SAE). If participant is being discharged prior to day 14 they will go home and continue with the treatment plan.

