# 8 PHARMACOVIGILANCE

#### 8.1 DEFINITIONS

Adverse Event (AE): any untoward medical occurrence in a patient or clinical trial subject administered a medicinal product and which does not necessarily have a causal relationship with this treatment. An AE can therefore be any unfavourable and unintended sign (including an abnormal laboratory finding), symptom, or disease temporally associated with the use of an investigational medicinal product (IMP), whether or not considered related to the IMP.

Adverse Reaction (AR): all untoward and unintended responses to an IMP related to any dose administered. All AEs judged by either the reporting investigator or the sponsor as having reasonable causal relationship to a medicinal product qualify as adverse reactions. The expression reasonable causal relationship means to convey in general that there is evidence or argument to suggest a causal relationship.

**Unexpected Adverse Reaction:** an AR, the nature or severity of which is not consistent with the applicable product information (e.g. investigator's brochure for an unapproved investigational product or SmPC for an authorised product). When the outcome of the adverse reaction is not consistent with the applicable product information this adverse reaction should be considered as unexpected. Side effects documented in the SmPC which occur in a more severe form than anticipated are also considered to be unexpected.

**Serious Adverse Event (SAE)** or **Serious Adverse Reaction (SAR):** any untoward medical occurrence or effect that at any dose:

- Results in death.
- Is life-threatening refers to an event in which the subject was at risk of death at the time of the event; it does not refer to an event which hypothetically might have caused death if it were more severe.
- Requires hospitalisation, or prolongation of existing inpatients' hospitalisation.
- Results in persistent or significant disability or incapacity.
- Is a congenital anomaly or birth defect.

Medical judgement should be exercised in deciding whether an AE/AR is serious in other situations. Important AE/ARs that are not immediately life-threatening or do not result in death or hospitalisation but may jeopardise the subject or may require intervention to prevent one of the other outcomes listed in the definition above, should also be considered serious.

**Suspected Unexpected Serious Adverse Reaction (SUSAR):** any suspected adverse reaction related to an IMP that is both unexpected and serious.

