#### **SAEs**

An SAE form should be completed and faxed to the study coordination centre for all SAEs within 24 hours. However, relapse and death due to <condition>, and hospitalisations for elective treatment of a pre-existing condition do not need reporting as SAEs.

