2.8 Serious adverse events

Incidence of venous thromboembolism and serious adverse events will be collected in this study to assess safety.

The proportion of participants experiencing a venous thromboembolism will be summarised by treatment arm and summaries of the time since randomisation will be presented. The number of readmissions will also be extracted from free text in SAE reports and will be summarised by treatment arm.

Serious adverse events coded as per the CTCAE will be summarised at the preferred term level and body system class. Events will be tabulated by treatment arm including information on the number with at least one event and the number of events to account for recurrent events.

Raw data for each SAE will be listed with information on event type, timing duration and outcome.

All above analysis will be undertaken for stage I and stage II

For stage II analysis we will also undertake the following analysis:

In addition, incident rate ratios for each event between treatment arms (RUX vs SOC or FOS vs SOC) with corresponding 95% CI will be calculated to account for differential follow-up and recurrent events with 95% CIs using a suitable model e.g. a negative binomial model or ZIP as appropriate. These results will be presented in both a table and graphically using a dot plot.

For events where time-to-event analysis is deemed appropriate we will present Kaplan-Meier plots with extended at risk tables for events that occur once within participants and mean cumulative function plots where events can recur within participants.^{1,2}

Blood measurements will be analysed as continuous outcomes calculating a mean difference and 95% CIs over the study follow-up period using a linear mixed effect model and the between arm effect will be plotted over time. Participants will be included as a random intercept with fixed effects for treatment arm, time and baseline outcome values. Stratification variables age and site, plus receipt of known effective treatments dexamethasone and/or tociluzimab, prior vaccination against COVID-19 and receipt of paxlovid and/or molnupiravir at the time of or prior to randomisation into MATIS will also be included as fixed effects. These outcomes will also be categorised as abnormal/normal and analysed using the distributional approach to retain power at day 14 and 28.3

3. Data analysis plan - Inferential analysis

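### 28-day readmission is taken only from SAE free text, and the protocol conflicts on whether a COVID-19 readmission needs an SAE form, so the count may be incomplete and may be captured unequally between arms

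*SAP*

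**What the plan says.** SAP 1.1.3 includes readmission among the outcomes to be compared between RUX or FOS and SOC: "were they readmitted within 28 days? (from free text in SAEs". SAP 2.8 gives the analysis: "The number of readmissions will also be extracted from free text in SAE reports and will be summarised by treatment arm". The inferential list in SAP 3.2 does not include readmission, so the outcome is descriptive only.

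The protocol sections that decide whether a readmission produces an SAE form are these:

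- **8.1** counts an event as serious if it "Requires hospitalisation, or prolongation of existing inpatients' hospitalisation".
- **8.4, under SAEs,** asks for a form for every SAE. Its next sentence makes an exception: "relapse and death due to <condition>, and hospitalisations for elective treatment of a pre-existing condition do not need reporting as SAEs". The bracketed word is a template placeholder that was not filled in.
- **7.16** says that participants may be "discontinued from treatment earlier due to unacceptable toxicity or disease progression which will be recorded as Serious Adverse Event (SAE").
- **8.5** names suspected serious adverse reactions and deaths as the events to record, and says other non-serious events will not be recorded.
- **11.4** requires collection of all SAEs and all non-serious AEs, and Table 7 schedules SAE collection at every visit.

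**The concern.** If the SAE form is the only route by which a readmission enters the data, the outcome is only as complete as the SAE rules make it. Those rules do not agree for readmission caused by COVID-19. A site that follows the exemption in 8.4 may submit no form, and the readmission then does not exist for the SAP.

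There is also an arm issue. The route in 7.16 depends on a study treatment that can be stopped, and SOC patients have none. If some COVID-19 readmissions reach a form by that route and the rest are treated as exempt, the drug arms will show more readmissions than SOC at the same true rate. SAP 2.8 also estimates incidence rate ratios for SAEs against SOC with 95% confidence intervals, so the same imbalance could enter a safety comparison. The trial is open label, so sites know the arm when they decide whether to complete a form.

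**Working it through.** **Step 1: is there another in-trial source?** The follow-up items in Protocol 9.1 are vital status, inpatient or discharged status with discharge date, ventilation and renal support. No readmission item is listed. Sections 9.1 and 9.2 allow collection to end at discharge. Section 3 plans weekly calls to day 28, but the Table 7 footnote makes post-discharge visits optional and calls conditional on feasibility, and neither place specifies a readmission question. The SAE form is the only stated source.

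**Step 2: what do the rules require for a participant readmitted with COVID-19 on, say, day 10?**

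| Rule | RUX or FOS | SOC |
|---|---|---|
| 8.1, first sentence of 8.4 (SAEs), 11.4: hospitalisation is an SAE, all SAEs reported | Form | Form |
| 8.4 exemption, if the placeholder means COVID-19 | Form not needed | Form not needed |
| 7.16: treatment stopped for progression | Form, if treatment is stopped for that reason | Cannot apply |
| 8.5: suspected serious reaction attributed to a study treatment | Form, if so attributed | Cannot apply |

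The first two rows contradict each other but are even across arms. The last two rows can operate only in the drug arms. Unequal capture arises if sites apply the exemption and also follow 7.16 or 8.5.

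**Step 3: illustration of size.** The documents give no readmission rate and no capture rate, so there is no plan figure to reproduce. Let r be the true readmission risk (equal in all arms), c the share of readmissions due to COVID-19, and k the share of those that reach an SAE form. All three are assumptions. Other readmissions are taken as fully captured.

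- Recorded risk = r × [(1 − c) + c × k]
- Recorded risk ratio (RR) = [(1 − c) + c × k(drug)] / [(1 − c) + c × k(SOC)], so r cancels
- Share missed in an arm = c × (1 − k)

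For counts, take r = 10% and the maximum 152 per arm (SAP 1.5.2), giving 15.2 true readmissions per arm and a true RR of 1.00.

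| c | k on SOC | k on drug | Recorded, SOC | Recorded, drug | RR |
|---|---|---|---|---|---|
| any | 1 | 1 | 15.2 | 15.2 | 1.00 |
| 0.5 | 0 | 0 | 7.6 | 7.6 | 1.00 |
| 0.5 | 0 | 0.25 | 7.6 | 9.5 | 1.25 |
| 0.5 | 0 | 0.50 | 7.6 | 11.4 | 1.50 |
| 0.7 | 0 | 0.25 | 4.6 | 7.2 | 1.58 |
| 0.7 | 0 | 0.50 | 4.6 | 9.9 | 2.17 |
| 0.9 | 0 | 0.25 | 1.5 | 4.9 | 3.25 |
| 0.9 | 0 | 0.50 | 1.5 | 8.4 | 5.50 |

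At c = 0.5 the arithmetic is (0.5 + 0.5 × 0.25)/0.5 = 0.625/0.5 = 1.25, and (0.5 + 0.5 × 0.50)/0.5 = 0.75/0.5 = 1.50. The larger ratios at c = 0.9 rest on a recorded SOC count of 1.5 and show only that the result is driven by the assumptions.

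Two facts follow. Under-recording that is the same in every arm loses events (half of them at c = 0.5, k = 0) but leaves the ratio at 1.00. A spurious difference needs unequal capture.

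**The case against.** The strongest reply is that the general rules already cover this. Hospitalisation is a seriousness criterion without regard to arm, a form is required for all SAEs, SAEs are sought at every scheduled visit, and discharged patients are to be telephoned weekly. A site working from those sections reports every readmission, and nothing is lost. That is a fair reading, and it is why the defect is a conflict and not a proven loss. It does not settle the matter, because the exemption stands in the sentence directly after the all-SAEs rule.

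Other points on that side also stand:

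- The exemption does not name COVID-19, and it permits non-reporting without forbidding a form.
- The exemption in 8.5 for consequences of COVID-19 concerns expedited reporting only.
- Progression need not end treatment: 7.4 describes giving fostamatinib by feeding tube to intubated subjects. The 7.16 route would therefore catch only some COVID-19 readmissions on drug.
- Any imbalance by these routes adds events to the drug arms, so it would not manufacture a benefit.
- Section 9.1 lets staff consult notes, routine systems and registries, and 3.3 and 9.3 collect admissions over the longer term. But the SAP does not draw on these for the 28-day outcome. The case report form is not among the documents, so a readmission field cannot be ruled out, although the SAP's reliance on free text suggests there is none.

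A reader might infer more: that progression is an SAE only when study drug is stopped, so that COVID-19 readmissions are lost on SOC and recorded on drug. The documents do not support this. Section 7.16 contains no such restriction, and 8.1, 8.4 and 11.4 point to reporting in every arm.

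**Conclusion.** The point holds in conditional form. SAE free text is the only stated source for a listed secondary outcome, and the protocol contradicts itself on whether a COVID-19 readmission must reach an SAE form. The count may be incomplete. It may also be captured unequally, since the 7.16 route, like attribution to a study treatment under 8.5, cannot apply to SOC. The SAE rate ratios in SAP 2.8 could carry the same asymmetry.

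The size cannot be derived from the documents. With equal true rates the recorded RR is 1.00 whenever capture is equal. It is 1.25 to 1.50 if half of readmissions are due to COVID-19, none of those is captured on SOC, and 25% to 50% are captured on drug. These figures illustrate a mechanism and do not estimate a bias. It would go too far to say that the count does miss readmissions, or that it does differ by arm.

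The consequence is limited, because readmission is summarised by arm and not tested, and the primary analysis does not use this count. The remedy is cheap enough to justify the change.

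**What to change.** 1. Record readmission (yes or no, date, cause) as an outcome item for every participant in all three arms, at the day 14 and day 28 contacts or from hospital records. Replace the free-text source in SAP 1.1.3 and the matching sentence in SAP 2.8 with this item.
2. Fill the placeholder in Protocol 8.4, and reconcile 7.16, 8.1, 8.4, 8.5 and 11.4 so that progression or relapse of COVID-19 is recorded in the same way in all arms. Whether that is as an outcome or as an SAE is for the trial team to decide; the statistical need is that the rule be the same in each arm.

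The cost is one data item, a little more data entry, wording changes in both documents, and a retrospective check for readmissions among participants already enrolled. A side benefit is that Protocol 4.2 treats discharge before day 14 as freedom from the primary event unless other data show otherwise, and a recorded readmission with its date and cause would supply such data.
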